1.2 Secondary Objectives

- 1.2.1 To determine the overall response rate to poly-ICLC in the treatment of children with recurrent low grade gliomas; tumor assessments are to be performed per 3D measurements.
- 1.2.2 Progression free survival over the course of the study.
- 1.2.3 Overall survival at 6 months – the time from starting study therapy to death from any cause.
- 1.2.4 To assess the toxicity associated with treatment with poly-ICLC in pediatric patients with recurrent low grade gliomas.
- 1.2.5 To study the effect of treatment with poly-ICLC on the signaling pathways controlling apoptosis in low grade glioma tumor cells.
- 1.2.6 To determine if surrogate markers of tumor response and progression can be identified in the serum, PBMC and/or cerebrospinal fluid of patients with recurrent low grade gliomas treated with poly-ICLC. Proteomics analysis will be performed to obtain protein levels of these markers such as OAS, interferon α , β , γ , PKR kinase, phosphorylation state of eIF2a, and induction of p21^{waf-1}.

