It was subsequently shown that low doses were better than higher ones for enhancing immune effects, and that the higher dose actually inhibited a number of cell-associated immune functions. It was also found that intramuscular injection brought about a much milder set of side effects. The most common complaint is a mild, transient discomfort at the injection site. On occasion, 8-12 hours after doses of 10 to 50 mcg/kg IM, patients may also develop a mild flu like syndrome with fever of less than 38°C which may last for another 12 hours, but responds readily to acetaminophen or aspirin. Mild myalgia, arthralgia, sometimes nausea, and malaise are present during this period of time. This flu-like syndrome typically diminishes markedly after the first little poly-ICLC treatment. Hepatic enzyme elevations are not typically seen at these dosages. Several multiple sclerosis or malignant glioma patients at Walter Reed Army Medical Center (WRAMC) have been maintained on regular intramuscular poly-ICLC for as long as 12 years without significant adverse effects. On very rare occasions in the course of treatment patients who have been tolerating treatments uneventfully may develop a more pronounced fever with chills and malaise (typical of higher dose IV poly-ICLC) in response to a single IM injection on subsequent dosing. This will typically respond to aspirin or acetaminophen and does not recur on repeated dosing. Whether it represented inadvertent IV injection on those occasions is uncertain. In a previous pediatric study conducted by the Principal Investigator, there was no dose limiting toxicity seen over 3 years in 45 children at doses of 20-30 micrograms/kg given 2 times a week as intra-muscular injection.

Summary of Poly-ICLC Toxicity data reported to FDA, 2005:

In the two recent, ongoing multi-center NIH consortium studies in adult glioblastoma patients and in patients with multiple-recurrent anaplastic glioma, most patients (N=62) reported at least one adverse event. The majority of adverse events were classified as either grade 1 (63%) or grade 2 toxicity (28%). The reported grade 3 and grade 4 toxicities were 8% and 0.8% respectively. Only two grade 5 events were reported, which were not assessed to be related to the study drug. The most frequently reported events (toxicities) were fatigue, pain, and myalgia. Very transient elevated liver enzymes, mainly grade 1 or 2, were also reported in fourteen patients.

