9.0 STATISTICAL CONSIDERATIONS

a. The primary goal of this trial is to obtain preliminary estimates of the ability of poly-ICLC to prevent or delay disease progression in subjects with recurrent or newly diagnosed low-grade gliomas. The primary endpoint will be progression free survival rate at 6 months (PFS6) after starting therapy. Progression free survival is defined as the time from starting study therapy to tumor progression, tumor recurrence, death from any cause, or occurrence of a second malignant neoplasm. Tumor assessment for the primary endpoint will be based on modified McDonald's criteria (section 7.1.2). Tumor assessment results obtained based on the 3D measurements will be considered secondary. The overall response rate (ORR) at 6 months will be a secondary endpoint. The ORR will include complete response, partial response, and stable disease (see Section 7.1.4). Time to progression will be documented for all patients who progress.

b. The second goal is to further define the side effects and toxicity of this regimen in these subjects. Secondary endpoints also include tumor ORR at 2 years after starting therapy and also the duration of the good response. Tumor response will be assessed at 3, 6, 9, 12, 18, 24 months after starting the therapy, as well as at the time of going off study if prematurely. Other secondary endpoints also include tumor response rates based on 3 dimension measurements as in section 7.1.3 at 3, 6, 9, 12, 18, 24 months after starting the therapy, progression free survival and overall survival over the course of the study.

c. The third goal will be to examine a series of biochemical determinations (e.g. serum OAS and interferon levels, PKR, phosphorylation state of eIF2a, p21^{waf-1}) as surrogate markers for sensitivity of patients to poly-ICLC. These will be compared to clinical response data. A subset of the proteins involved in apoptosis and signaling pathways will be looked into specifically to assess the effect of the study treatment on these signaling pathway changes. The specific endpoints are:

- Association of baseline levels of proteins (such as OAS, interferon, PKR, phosphorylation state of eIF2a, p21^{waf-1}) in serum, PBMC and/or cerebrospinal fluid with tumor response status at 6 months after treatment with Poly-ICLC.

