9.1.6 Accrual and study duration

All the 23 patients are expected to be accrued in 3 years and the total study duration will be about 5 to 5.5 years.

9.2: Analysis of Results

9.2.1: Analysis of anti-tumor activity

The "best response" rate is defined as the percent of evaluable subjects who experience a CR or PR or SD (see Section 7.1.2). The best response rates as well as overall response rates at 6 and 24 months will be estimated and exact lower one sided confidence intervals for the true response rates will be presented (Jung, 2004). The duration of response for each subject that has tumor response will be summarized in a table. The same analysis will be done for the tumor response rate based on 3 dimension measurements as in section 7.1.3.

9.2.2: Summary of toxicities and side effects

All observed toxicities and side effects will be recorded on toxicity sheets and the data collection forms. Toxicity information including type, severity, time of onset and resolution, and probable association with the study drugs will be recorded. Toxicities will also be analyzed by NF1 status (NF1 vs. non NF1 subject cohorts). Tables will be constructed to summarize the observed incidence by type of toxicity and severity.

9.2.3: Analysis of Survival

Overall survival and progression-free survival rates will be estimated using the Kaplan-Meier method (Kaplan, 1958).

9.2.4: Analysis of biochemical measures.

Laboratory studies will be done on subject's serum and peripheral blood drawn prior to and at two weeks after starting treatment with Poly ICLC. Levels and changes in the measurement of serum markers and proteins such as OAS, interferon α , β , γ , PKR kinase, eIF2a, and p21^{Waf-1} will be determined via proteomic analysis. For each marker, a Fisher's exact test or a Wilcoxon rank sum test will be used to assess the association of a baseline protein level or changes from baseline against tumor response status at 6 months. A log rank test will be used if the outcome is progression free survival.

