Relationship/attribution: The Investigator will be asked to document his/her opinion of the relationship of the event to study medication as follows:

- 1) *Unrelated*: The adverse event is clearly not related to the investigational agent(s).
- 2) *Unlikely*: The adverse event is doubtfully related to the investigational agent(s).

- 3) *Possible*: The adverse event may be related to the investigational agent(s).
- 4) *Probable*: The adverse event is most likely related to the investigational agent(s).
- 5) *Definite*: The adverse event is clearly related to the investigational agent(s).

10.1: Reporting Adverse Drug Reactions Occurring with Investigational Agents

Within 24 hours of recognition, contact the Principal Investigator or his designee by telephone to verify the identification process and the existence of an adverse drug reaction or toxic death.

The following data **must** be reported to the study PI:

- Subject identification number
- Presenting diagnosis, Description of event
- Laboratory data supporting event
- Total and daily doses of suspected drug
- Time of event
- Type and grade of adverse event
- Methods used to recognize and characterize the effect
- Physician attribution/relationship of event to study drug (see above)

The participating site must then submit a completed adverse event case report form to the coordinating site.

Within 10 days of the adverse event, a completed NCI Adverse Reaction Form for Investigational Agents with the NCI protocol number should be submitted to the IRB for life threatening (Grade 4) and fatal known reactions (except Grade 4 myelosuppression) or any unexpected, unanticipated Grade 2 and 3 reactions that are possibly, probably, or definitely attributed to the study drug.

A completed (NCI) Adverse Reaction Form for Investigational Agents should be sent electronically or by FAX to the FDA (see Appendix IV for the electronic links). Oncovir will be notified as soon as an adverse event form has been submitted.

10.2: Toxicity Criteria.

The NCI Common Terminology Criteria for Adverse Events (CTCAE) version 4.0 will be used and referenced. The site, measure, grade, relationship, action taken, and outcome for all toxicities (grades 3 and 4 as well as any unexpected, unanticipated Grade 2 reactions that are possibly, probably, or definitely attributed to the study drug) are to be reported on the appropriate toxicity monitoring and adverse event forms.

10.3: Data Safety Monitoring

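### Sections 9.2.2 and 10.2 set conflicting scopes for toxicity data, and nothing says which governs the routine toxicity monitoring form

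*Combined protocol and SAP*

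**What the plan says.** Toxicity is a stated purpose of the trial. Objective 1.2.4 reads "To assess the toxicity associated with treatment with poly-ICLC in pediatric patients with recurrent low grade gliomas", and section 9.0(b) adds "The second goal is to further define the side effects and toxicity of this regimen in these subjects".

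Section 9.2.2 sets the scope of the data without any grade limit: "All observed toxicities and side effects will be recorded on toxicity sheets and the data collection forms". It asks for an analysis by NF1 status and says "Tables will be constructed to summarize the observed incidence by type of toxicity and severity".

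Section 10.2 adopts CTCAE version 4.0 and lists the details wanted for toxicities, but a parenthesis restricts these to "grades 3 and 4 as well as any unexpected, unanticipated Grade 2 reactions" with at least a possible attribution to the drug. The details for that restricted set "are to be reported on the appropriate toxicity monitoring and adverse event forms".

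Sections 5.2F and 5.3F call for the toxicity monitoring form at week 2, before each cycle and at end of therapy or relapse. They give no grade threshold. Section 10.0 says that adverse reaction reporting comes on top of the study's toxicity data and does not replace it.

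**The concern.** Both sections speak of all toxicities, and both direct them to toxicity forms, but one covers every grade and the other a subset. The plan does not say whether the toxicity sheets of 9.2.2 are the toxicity monitoring forms of 10.2, or which section prevails if they are. A site coordinator could reasonably fill in the routine form to either scope.

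The difference falls on the events this drug is expected to produce. Section 6.0 lists injection-site discomfort, malaise, myalgia and fever as its side effects. Because they are expected, 10.2 leaves them out at grade 2 as well as at grade 1. Section 2.2 reports that patients with NF1 had more side effects, fever and erythema above all, and section 4.1 separates the NF1 and non-NF1 cohorts for the analysis of toxicity. That comparison therefore leans on events that 10.2 would leave off the form. With two sites and 23 subjects, a difference in reading between sites could also pass for a difference between cohorts. Low-grade events that are not captured at the visit are hard to recover reliably afterwards.

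**Working it through.** **The passages side by side**

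- 9.2.2: all toxicities and side effects; toxicity sheets and data collection forms; type, severity, onset, resolution and association.
- 10.2: grades 3 and 4, plus grade 2 that is both unexpected and at least possibly attributed; toxicity monitoring and adverse event forms; site, measure, grade, relationship, action and outcome.
- 5.2F and 5.3F: the toxicity monitoring form is completed at routine visits, with no threshold.
- 10.1: expedited reporting has its own thresholds (grade 4 and fatal known reactions other than grade 4 myelosuppression, and unexpected grade 2 and 3 reactions that are at least possibly related). Section 10.2 is therefore not a restatement of the expedited rule.

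**Size of the difference**

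The only grade distribution in the documents is in section 2.3, in the summary of toxicity data reported to the FDA in 2005. It covers two adult glioma studies (N = 62): grade 1 63%, grade 2 28%, grade 3 8%, grade 4 0.8%, and two grade 5 events. Event counts are not given, so the figures can only be checked for consistency:

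63 + 28 + 8 + 0.8 = 99.8%. Rounding and the two grade 5 events can account for the remainder.

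Let f be the fraction of grade 2 events that are both unexpected and attributed. The documents do not give f, so it is varied from 0 to 1.

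Share left off the form under 10.2 = [63 + 28 × (1 − f)] / 99.8

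- f = 0: 91 / 99.8 = 91%
- f = 0.25: 84 / 99.8 = 84%
- f = 0.5: 77 / 99.8 = 77%
- f = 1: 63 / 99.8 = 63%

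The share kept runs from 8.8 / 99.8 = 9% (f = 0) to 36.8 / 99.8 = 37% (f = 1). Grade 1 alone is more than half, so a majority is omitted at every value of f. If 9.2.2 governs, nothing is omitted.

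A second figure in section 2.3 points the same way. Of the 18 events of grade 2 or higher that were definitely or probably related, 17 were grade 2 and one was grade 3. So 17/18 = 94% of these would reach a form limited by 10.2 only if judged unexpected.

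**The case against.** The best defence is that the two sections are tiers. Section 9.2.2 says recorded and 10.2 says reported; they ask for different fields; and 10.0 shows that the plan treats study toxicity data as a stream of its own. On that reading 10.2 asks for extra detail on a more serious subset, and the data collection forms, submitted monthly under section 5.0, still carry every toxicity. The coordinating site also reviews forms and source documents monthly, and the study committee reviews toxicities monthly (10.3.2).

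Much of this stands. It shows that the loss is not certain. It does not settle the conflict, because 10.2 names the routine form itself, and the statement in 10.0 does not help if 10.2 is what sets the scope of toxicity reporting. Monthly review might expose a divergence between sites, but it supplies no rule for resolving it.

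A reader might infer more than the documents support:

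- That low-grade data will be lost. This happens only if a site puts 10.2 above 9.2.2, and nothing in the plan says that sites complete their forms from section 10.
- That the toxicity objective is defeated or the tables left nearly empty. Grades 3 and 4 stay on the 10.2 list, and 9% to 37% of events would remain on the adult split. Cycle 1 temperatures are logged under 4.1, and blood counts and chemistry are scheduled before each cycle.
- That fatal toxicity goes unreported because the parenthesis omits grade 5. Toxic deaths are covered in 10.0 and 10.1, and a death report form is required in 5.3G.

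**Conclusion.** The inconsistency is real and should be corrected. It is an unreconciled conflict of wording about the scope of the routine toxicity form, and the loss is conditional. If 10.2 is followed, 63% to 91% of events would be absent from that form; if 9.2.2 is followed, none would be.

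The range rests on two assumptions: that the grade split in adults with malignant glioma applies to children with low-grade glioma, and that f may lie anywhere from 0 to 1. It also takes the attribution condition in 10.2 to apply to grade 2 only, which is the natural reading. If it were read as covering grades 3 and 4 too, unrelated events of those grades would also drop out.

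The stopping rule in 9.1.3 uses grades 4 and 5, and the general dose rule in 4.2 uses grades 3 and 4, so neither depends on the events at issue. What is exposed is the low-grade side-effect profile and the NF1 versus non-NF1 toxicity comparison.

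**What to change.** In 10.2, state that toxicities of all grades (1 to 5), whatever the attribution, are recorded on the toxicity monitoring form at each scheduled toxicity evaluation, as 9.2.2 requires. Confine the grade and attribution limits to the adverse event form. Use one name for the toxicity sheet or form throughout, so that 5.2F, 5.3F, 9.2.2 and 10.2 plainly refer to the same document.

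The cost is about a sentence of text and some extra data entry. No visits are added: section 5.0 already schedules toxicity evaluation at day 15 of cycle 1, before each later cycle and at end of therapy.

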10.3.1 Data and Safety Monitoring Board

This study will be monitored in accordance with the UCSD/Rady Children's Hospital plan for data and safety monitoring of Phase 1 and 2 studies. This study will use the UCSD Moores Cancer Center DSMB. In brief, the role of the Data and Safety Monitoring Board is to protect the interests of patients and the scientific integrity for all Phase 1 and 2 studies. The DSMB consists of 7 members including a chair, a statistician, and a pharmacist. The DSMB meets on a regular basis to review current study results, as well as data available to the DSMB.

from other related studies. The DSMB will provide recommendations for each study reviewed to change the study or to continue the study unchanged. Data and Safety Board reports for institutional review boards will be prepared.

10.3.2: Study Monitoring

The Principal Investigator will monitor the study regularly to validate subjects' eligibility, evaluability, and any toxicities that are entered in the study database. In addition, the study committee comprised of the coordinating site members and at least 2 members of the participating site via phone conference will discuss and review once a month the enrolled subjects, toxicities, and integrity of data collection.

Monitoring of Source Documents:

The participating site will submit case report forms and copies of necessary supporting clinical source documents to the coordinating site for review of data accuracy prior to data submission. This will occur at a monthly interval from the time of subject's enrollment into the study.

Additionally a member of the DSMB at the coordinating site will monitor the data collection and the source documentation of all subjects enrolled at the enrolling sites. This monitoring will review protocol compliance, drug accountability, and adverse event reporting as well as regulatory compliance annually.

10.4: FDA Annual Reporting

Oncovir, the IND holder of the study drug, will submit an annual report to the FDA. This report will include de-identified aggregate data from this study as well as compiled NCI adverse event reports.

11.0: REFERENCES

Black K, K. Chen, et al. (1992). Inflammatory leukocytes associated with increased immunosuppression by glioblastoma. *Journal of Neurosurgery* 77:120-126.

Blyth CR, Still HA (1983). Binomial confidence intervals. *Journal of the American Statistical Association* 78:108-116.

APPENDIX I

PERFORMANCE STATUS SCALES/SCORES

PERFORMANCE STATUS CRITERIA

Karnofsky and Lansky performance scores are intended to be multiples of 10

ECOG (Zubrod)		Karnofsky		Lansky*	
Score	Description	Score	Description	Score	Description
0	Fully active, able to carry on all pre-disease performance without restriction.	100	Normal, no complaints, no evidence of disease	100	Fully active, normal.
		90	Able to carry on normal activity, minor signs or symptoms of disease.	90	Minor restrictions in physically strenuous activity.
1	Restricted in physically strenuous activity but ambulatory and able to carry out work of a light or sedentary nature, e.g., light housework, office work.	80	Normal activity with effort; some signs or symptoms of disease.	80	Active, but tires more quickly
		70	Cares for self, unable to carry on normal activity or do active work.	70	Both greater restriction of and less time spent in play activity.
2	Ambulatory and capable of all self-care but unable to carry out about more than 50% of waking hours	60	Required occasional assistance, but is able to care for most of his/her needs.	60	Up and around, but minimal active play; keeps busy with quieter activities.
		50	Requires considerable assistance and frequent medical care.	50	Gets dressed, but lies around much of the day; no active play, able to participate in all quiet play and activities.
3	Capable of only limited self-care, confined to bed or chair more than 50% of waking hours.	40	Disabled, requires special care and assistance.	40	Mostly in bed; participates in Quiet activities.
		30	Severely disabled, hospitalization indicated. Death not imminent.	30	In bed; needs assistance even for Quiet play.
4	Completely disabled. Cannot carry on any self-care. Totally confined to bed or chair.	20	Very sick, hospitalization indicated. Death not imminent.	20	Often sleeping; play entirely limited to very passive activities.
		10	Moribund, fatal processes progressing rapidly.	10	No play; does not get out of bed.

*The conversion of the Lansky to ECOG scales is intended for NCI reporting purposes only.

APPENDIX II: Criteria for Type 1 Neurofibromatosis:

- Clinical diagnosis requires the presence of at least 2 of 7 criteria to confirm the presence of NF1. Many of these signs do not appear until later childhood or adolescence, and thus confirming the diagnosis often is delayed despite a suspicion of NF1. The 7 clinical criteria used to diagnose NF1 are as follows:
 - Six or more café-au-lait spots or hyperpigmented macules greater than or equal to 5 mm in diameter in children younger than 10 years and to 15 mm in adults
 - Axillary or inguinal freckles
 - Two or more typical neurofibromas or one plexiform neurofibroma
 - Optic nerve glioma
 - Two or more iris hamartomas (Lisch nodules), often identified only through slit-lamp examination by an ophthalmologist
 - Sphenoid dysplasia or typical long-bone abnormalities such as pseudarthrosis
 - First-degree relative (eg, mother, father, sister, brother) with NF1

<http://www.emedicine.com/neuro/topic248.htm>

APPENDIX III: List of Anticonvulsants Based on CYP3A/4/5 Enzyme Induction

**Anticonvulsant drugs with little or no enzyme induction:
ELIGIBLE for concomitant use in study.**

Generic Name	Trade Name
Gabapentin	Neurontin
Lacosamide	Vimpat
Lamotrigine	Lamictal
Levetiracetam	Kepra
Tigabine	Gabitril
Topiramate	Topamax
Valproic Acid	Depakote, Depakene
Zonisamide	Zonegran

**Enzyme inducting anticonvulsant drugs (EIACD):
NOT ELIGIBLE for concomitant use in study.**

Generic Name	Trade Name
Carbamazepine	Tegretol
Felbamate	Felbatol
Phenobarbital	Phenobarbital
Phenytoin	Dilantin
Primidone	Mysoline
Oxcarbazepine	Trileptal
Rufinamide	Banzel

